The sample size calculation is based on the expected percent of men engaging in high risk behavior after 6 months of follow-up, accounting for the intraclass correlation coefficient (ICC) and estimates of unprotected sex estimated from our pilot dataset of 105 participants from four barbershops. Unprotected sex, defined in this example as two or more sexual partners in the past three months plus at least one episode of unprotected vaginal or anal sex, was reported by 42% of our sample in a previous pilot study of the program. Assuming that 42% of the participants in the control group would engage in high risk behavior, an ICC of 0.03, and a minimum of 23 participants from each barbershop, the study has 80% power to detect an absolute reduction of 12% (relative reduction of 29%) in rates between the two groups with alpha=0.05, two-tailed and 15 barbershops for each intervention group (i.e., 30 clusters and 690 total participants). In order to achieve a sample size of 690 at the six-month follow-up, we estimate that we will need to recruit 875 men in order to account for a loss to follow-up as high as 20%.

Participants:

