Inclusion criteria include men age 18 or older who report two or more partners in the past six months, unprotected sex with a woman in the past six months, and identify as Black or African American. Exclusion criteria for participation include (1) having been in an HIV prevention research study in the last six months, (2) reporting a history in the past five years of injection drug use, (3) reporting a history in the past five years of having sex with other men, (4) reporting an HIV-positive serostatus, or (5) inability to understand spoken English. In order to ensure that our program meets the needs of a unique and understudied population, we have chosen to exclude men with an injection drug use history or who report same sex behavior, given that interventions have been developed for these populations and that the behavioral risk and determinants of risk are unique to these subpopulations. However, it is recognized that the very nature of being on the 'down low' would necessitate that some men who engage in same-sex relationships may not report this behavior and be included in the sample. Similarly, the stigmatized nature of injection drug use may be linked to underreporting during our screening and evaluation procedures. The risk in this scenario is that inclusion of men who for whom intervention messages are not tailored could dilute differences between the experimental and control group, but would not cause harm. We note that although we focus on men who identify as Black, some men will also report Latino ethnicity; these men will not be excluded from the study, as reflected in our planned enrollment table. However, given that our program is being completed in barbershops serving African American men, the vast majority of potential enrollees will be English-speaking. During a pilot test of the Barbershop Talk program, we found that of over 100 men who completed a screener, all were able to understand English. While this does not negate the fact that some non-English speaking men may have been less likely to agree to screener, it does speak to the project team's view that translation of all intervention sessions and evaluation measures would not be a worthwhile use of funds given that we are unlikely to be able to have a large enough number of non-English speakers in the sample to be able to draw conclusions about effectiveness in these sub-groups, and that the program was not tailored to what are likely the unique needs of men who are non-English speaking.

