
Recruitment procedures:

Recruitment will take place in barbershops. Customers will be introduced to study staff by their barber and asked whether they would be willing to meet with our research assistant to complete screening for the study. Given that we will be attempting to enroll all eligible customers within a recruitment period, we anticipate that enrollment at each barbershop will be approximately proportional to the size of that venue's total client pool. The research assistant will describe the study, and assess eligibility via an ACASI screening form with a privacy screen attached. All eligible participants who are interested in participating will provide individual, written, informed consent written at a level appropriate to our priority population. After receiving the information on the Consent Form appropriate for the barbershop condition, the potential participant can direct any additional questions or clarifications to the research assistant. Those who agree to join the study will sign the consent form and will be given a copy for their records, and will complete a locator form. Following the consent

procedure the participant will complete an ACASI administered baseline assessment, and will be provided study activities congruent with the experimental arm assigned at that barbershop. To reduce self-report bias, project staff responsible for recruiting and administering evaluation assessments do not administer intervention activities, and staff administering intervention activities do not administer assessments to those clients. The consent form is written at a Flesch-Kincaid grade level below 8.0.

Program Evaluation:

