Evaluation assessments will take place via ACASI, with all other data forms (e.g., locator, enrollment, contact logs, and final interview questions) completed manually. For the linked baseline, 3, and 6 month assessments, we will assign each study participant a unique study identification number and their name and study ID number will be linked on a Locator Form (which will provide detailed contact information for follow-up, and will help reduce the of participants enrolling more than once), on an Enrollment Log (which will provide date and location of enrollment and scheduled interviews), on a Contact Log (which will document contacts of the client with data collection staff) and in the local data management system. Locator Forms, Enrollment Logs, signed Consent Forms, and Contact Logs will be kept in locked file cabinets in a locked office in SUNY DMC. Data transmission will be tracked and monitored by the project coordinator. ACASI interview data will be encrypted during the ACASI interview as information is captured and saved on the computer's hard drive, which will be transmitted to the project coordinator daily. Computer programs will be developed to check data completeness and consistency. Each system file will have its own system dictionary containing variable names, labels, valid code values and labels and missing data definitions. The SUNY IS Division performs nightly automated backups on a Digital Linear Tape system. In addition, once each month a complete backup tape is made for offsite storage. All data stored on the servers are password protected and encrypted.

Data analysis:

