Statistical analysis will be performed by SAS version 9.2 (SAS Institute, Cary, NC). The primary analysis method for study outcomes to test the main effect of the *Barbershop Talk* intervention will be generalized estimating equations (GEE) models, accounting for the cluster randomization. A logit link function will be specified for binary outcomes (including the primary outcome of engaging in high risk behavior after 6 months of follow-up) while a identity link function will be specified for continuous outcomes. The effects of mediating and moderating variables will be tested by appropriate modeling methods (Jaccard, Turrissi et al. 1990; Shrout and Bolger 2002; MacKinnon, Fairchild et al. 2007). Generalized mixed effects models, treating barbershop as a random effect, will also be fit as sensitivity analyses. All statistical tests will be at the 5% (two-tailed) significance level for main effects and at the 10% (two-tailed) significance level for interactions, with no adjustment for multiple testing.

Timeline:

This is a five year study. We will spend the first six months of the study working with our community advisory board on issues of protocol development, on development and production of high quality graphics for the program, on training of study staff, on securing of IRB approvals for the work and recruiting barbershops. Given our past experience in the barbershops, and our recruitment goal of 875 men, we anticipate that we will enroll participants at the rate of 20-25 per month over a forty-two month period. This would carry our follow-up period through to month six of year five. In the last six months of year five, we will engage in data cleaning and analysis, and dissemination of research findings.

Human subjects considerations:

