
sponsor(s) of the study: The National Institute of Health (NIH); 2) The Institutional Review Board of SUNY Downstate Medical Center and the applicable DMC officials and staff who supervise the way research is done and run the business operations; 3) The research team for this study; and 4) The collaborating research agency, namely Arthur Ashe Institute for Urban Health.

The locator form, contact log, and enrollment form will be kept until the evaluation is completed, after which time they will be destroyed. At that time, we will also electronically shred the computer file linking the names and ID numbers. Laptop computers used to collect ACASI data will be protected during transport through the use of locked padded cases which will remain with the interviewers at all times. Data collection will occur in the barbershop; follow-up evaluations may also take place within a private space at SUNY Downstate. In summary, this is a low risk study, conducted in an area of elevated HIV risk. All participants, whether assigned to the intervention and control will receive some health education, but the question of the effectiveness of the intervention program on reducing sexual risk behavior is not known. Based on program elements, it is our hypothesis that the program will produce changes in skills and motivation for safer sex, in community and personal empowerment, and in interpersonal communication skills, but similarly this cannot be guaranteed.

References

Albarracin, D., J. C. Gillette, et al. (2005). "A test of major assumptions about behavior change: a comprehensive look at the effects of passive and active HIV-prevention interventions since the beginning of the epidemic." *Psychol Bull* **131**(6): 856-97.

Carey, M. P. and K. E. Schroder (2002). "Development and psychometric evaluation of the brief HIV Knowledge Questionnaire." *AIDS Educ Prev* **14**(2): 172-82.

CDC. (2011). "Diagnoses of HIV Infection and AIDS in the United States and Dependent Areas, 2009." *HIV/AIDS Surveillance Report, Volume 21* Retrieved March 21, 2011, from <http://www.cdc.gov/hiv/surveillance/resources/reports/2009report/>.

CDC. (2011). "HIV in the United States." Retrieved March 23, 2011, from <http://www.cdc.gov/hiv/resources/factsheets/us.htm>.

Darrow, W. W., J. E. Montanea, et al. (2009). "AIDS-related stigma among Black and Hispanic young adults." *AIDS Behav* **13**(6): 1178-88.

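### The six-month look-back does not bar men who received Barbershop Talk in the pilot, and the check on repeat enrolment has no eligibility rule behind it; the likely dilution is small

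*Protocol*

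**What the plan says.** Under Participants, the Protocol lists five exclusions. One concerns prior exposure: "having been in an HIV prevention research study in the last six months". The inclusion criteria require two or more partners, and unprotected sex with a woman, in the past six months.

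The same program had been tested before. Study design and sample size draws on "our pilot dataset of 105 participants from four barbershops", and the high-risk behaviour "was reported by 42% of our sample in a previous pilot study of the program". That section also says shops are randomised once a list of eligible shops has been compiled. It does not say whether the four pilot shops are on the list.

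Under Timeline, six months of preparation come first, and then "we will enroll participants at the rate of 20-25 per month over a forty-two month period".

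On repeat enrolment, Data management says that the Locator Form, which links name and study ID, "will help reduce the of participants enrolling more than once" (a word is missing in the text). Recruitment procedures places the form after ACASI screening and consent: those who join "will be given a copy for their records, and will complete a locator form". Human subjects considerations adds: "The locator form, contact log, and enrollment form will be kept until the evaluation is completed".

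**The concern.** The Protocol randomises shops rather than men because program content is meant to travel through shop networks and could reach controls. A man who attended the program in the pilot and is later recruited at a control shop is a direct case of the contamination that this design is meant to limit. In an intervention shop, a pilot man's baseline is already post-treatment, and he may have less left to gain. Either way the contrast between arms is pulled toward zero.

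A man enrolled twice raises a second problem. Both the Protocol's GEE models and the SAP's mixed models account for clustering by barbershop only, so a man entered at two shops would be analysed as two independent men.

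**Working it through.** **1. Does the six-month rule reach pilot men?** The pilot's end date is not given. If it ended before the study began, the six months of preparation use up the whole look-back before the first man is enrolled, and the rule excludes no pilot man. No other listed criterion refers to earlier receipt of the program.

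**2. Does anything stop re-entry within the trial?** The Locator Form is kept until the evaluation is completed, so it is available throughout enrolment. But it comes after screening, no step for matching names is described, and it is said only to help. If staff did find a match more than six months after a man's participation, no listed exclusion would apply to him. Control men attend a prostate cancer curriculum, so some might not report having been in an HIV prevention study at all (an inference).

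**3. How many pilot men could there be among controls?** Inputs from the Protocol: 105 men and 4 shops in the pilot; 875 men and 30 shops (15 per arm) in the trial.
- If every pilot man re-enrolled and they split evenly: 105/875 = 12% of each arm.
- The same by shop: 105/4 = 26 pilot men against 875/30 = 29 recruits per shop, so at most 26/29 = 90% of a pilot shop's recruits. If all four shops were on the list, 4 × 15/30 = 2 control shops are expected, and 2/15 × 0.90 = 12%.

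This is the figure for an even split; an uneven draw would raise the share in one arm and lower it in the other.

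**4. Dilution.** Let f be the share of controls previously exposed and r the share of the 12-point effect that they retain. Neither is in the documents; both are assumptions. With the intervention arm held at 30%, the difference is 12 × (1 − f × r). At f = 0.12 and r = 1 it is 12 × 0.88 = 10.56 points.

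**5. Power.** The plan states 80% for 42% versus 30%, ICC 0.03, 23 men per shop, 15 shops per arm and two-sided alpha 0.05. The design effect is 1 + 22 × 0.03 = 1.66, and the effective size is 345/1.66 = 207.8 per arm. The standard two-proportion normal formula then gives 72.3%, not 80%. That shortfall is a separate matter; here 72.3% serves only as the base.

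| f | r | Difference (points) | Power |
|---|---|---|---|
| 0 | – | 12.00 | 72.3% |
| 2% | 0.5 | 11.88 | 71.5% |
| 5% | 0.5 | 11.70 | 70.2% |
| 5% | 1 | 11.40 | 68.0% |
| 12% | 0.25 | 11.64 | 69.8% |
| 12% | 0.5 | 11.28 | 67.1% |
| 12% | 1 | 10.56 | 61.6% |

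**The case against.** The strongest reply is that the inclusion criteria already do much of the work. Every entrant must report multiple partners and unprotected sex in the past six months, which is close to the primary outcome itself. Pilot men who kept the benefit are largely screened out, and those who qualify are still at risk. This stands, and it makes r = 1 implausible; some residual effect remains possible.

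The number exposed is also uncertain. The 105 men are a dataset. Elsewhere the Protocol mentions over 100 men who completed a screener and 78 on whom recruitment, screening, consent and baseline procedures were piloted. Nowhere does it say how many attended the program. This stands too: 105 is an upper bound.

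Three stronger readings are tempting, and the documents do not support them:
- *Men who complete this trial are simply eligible again, in either arm.* The Locator Form shows that repeat enrolment was foreseen and unwanted. A man returning to his own shop would get the same arm; crossing arms needs a second shop in the other arm and a failure to notice.
- *Most of the sample could re-enter.* Six months of follow-up plus six months of look-back leave 42 − 12 = 30 months, or 30/42 = 71% of accrual. That counts elapsed calendar time and is not an estimate of re-entrants. Recruitment procedures refers to a recruitment period, so a given shop may not stay open to recruitment for all 42 months.
- *Pilot shops will serve as controls.* The Protocol does not say that they are on the list. It does say that staff will observe shops and interview shop staff in connection with contamination.

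**Conclusion.** The gap in the eligibility rule is real. Followed as written, it does not bar men who received Barbershop Talk in the pilot, provided that at least six months have passed. For men already in this trial, the weakness is narrower: the safeguard exists, but its matching step is unstated and no criterion supports it beyond six months.

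The likely bias is small and toward no effect. The loss of about 1.4 points out of 12 requires every pilot man to have attended the program, returned, qualified and consented, with an even split between arms and a full lasting effect. At more moderate assumptions (5% of controls exposed, half the effect retained) the loss is 0.3 points and about 2 percentage points of power. It merits correction because it is avoidable at little cost and hard to undo after enrolment, not because it threatens the trial's conclusion.

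**What to change.** Split the first exclusion into two parts. Keep the six-month rule for other HIV prevention studies, and add an exclusion, without time limit, for anyone who ever took part in the Barbershop Talk pilot or in either arm of this trial at any shop. Put the question in the ACASI screener. State that names are checked against trial locator records before consent, and against pilot records if these were kept; the documents do not say whether they were. Leaving the pilot shops off the randomisation list is optional, since nothing shows that they were to be used.

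The cost is a protocol amendment, one screener item, a name check, and at most about 105 potential recruits.

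The SAP is dated August 2018 and written in the past tense, so enrolment may already be closed. In that case, the remaining step is to report how many men are known to be duplicates or pilot participants and to repeat the primary model without them, if the linking records survive. The Protocol has the locator forms destroyed after the evaluation.

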Hypothesis 1: Compared to men assigned to an attention control condition, those exposed to the intervention will have lower levels of sexual risk behavior at a 3 and 6 month follow-up.

Hypothesis 2: Compared to men assigned to an attention control condition, those exposed to the intervention will have improved outcomes at 3 and 6 months, on theoretically derived mediators of sexual risk behavior, including interpersonal factors such as attitudes, self-efficacy, communication skills and perceived norms around safer behavior, as well as on factors such as increased individual and community empowerment and decreased HIV-related stigma.

Aim 2: To examine individual and contextual-level factors that explain variation in the efficacy of the intervention.

Hypothesis 3: Intervention impact will be moderated by individual and contextual level-factors such as higher perceived basic needs and housing instability, incarceration and substance use history, higher perceived racism, and traditional gender role norms and attitudes, such that intervention effects will be reduced among men with these risk factors.

Project Rationale:

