Audio Computer-Assisted Self-Interview (ACASI) will be utilized to collect self-reported data at baseline (pre-intervention) and also at 3- and 6-month follow-up from the date of completion of the *Barbershop Talk* program. Respondents will listen to headphones and questions will be provided by a recorded voice stored in computer memory. The responses will be entered by pressing on the computer's touchscreen. A privacy screen will be utilized so that other barbershop customers cannot view responses, and headphones with disposable covers will be used so that respondents can listen to questions and answer options. Prior to baseline questions being administered, participants will complete a series of 'warm up' practice items. During our formative work, we piloted the recruitment, screening, consent and baseline procedures described in this project on 78 men and have found them to be feasible to implement, acceptable to barbershop personnel and clients, and a sound method for maintaining privacy and confidentiality. Additionally, at the 6-month interview participants will be asked to complete an additional set of questions to help identify the need for future programs. These final questions will be administered by a study staff in an interviewer led format. Questions 1-3 of the questionnaire pertain to existing knowledge about PrEP, and interest to receive more information about PrEP. In conjunction with these questions, study participants will be offered a PrEP brochure to increase their knowledge about HIV prevention. For question #4 of the interview a response card will be handed to study participants to facilitate the selection of their answers to that question. Participants will be reimbursed at \$20 for the baseline interview, \$30 for the three month follow-up assessment, and \$40 for the six month follow-up assessment, which is reasonable considering the length of the interview, and is in line with typical reimbursement levels for other HIV prevention program evaluations. The evaluation instruments will take approximately forty minutes to complete. All measures described in the following section have been selected based on their established reliability and validity in published HIV prevention studies and with adult African American populations.

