All measures included in the program evaluation have been selected based on their demonstrated reliability and validity in published research and in our own previous work in populations similar to the men in this study; we will pilot the instrument prior to administration. To examine hypothesis 1, our main outcome measure will be a composite measure of the proportion of respondents who report two or more partners in the last six months and report unprotected sex during this time. This outcome, which was reported by over 40% of our population in our formative work, is a more informative marker of risk than some other outcome measures used in HIV prevention trials (e.g., any unprotected vaginal or anal sex) in that it helps to differentiate persons engaging in unprotected sex in the context of a single monogamous partnership, versus those who are at higher risk for HIV infection. Other measures of risk will include (1) partner concurrency, (2) number of sexual partners, (3) condom use consistency, and HIV testing. Behaviors will be assessed over the previous three months. Of course, self-report measures of sexual risk behavior are prone to self-report bias as individuals are likely to inflate or deflate their responses based on factors such as gender norms around sexual behavior. However, we will engage in a number of activities to promote honesty in responses by (1) assuring men of the confidentiality of their responses and explain the system that will be used to ensure this, (2) stressing the importance of honest answers to the scientific integrity of the project and for informing community health, (3) and using ACASI. Responses on this measure will be correlated with measures such as sexual behavior and drug use to provide an estimate of the extent to which this bias contributes to scores. Often, clinic-based interventions are able to collect data on more 'hard' outcomes, such as STD rates. The ability to power these studies is based on the fact that participants at baseline typically have and are treated for STD, and that there are known and substantial risks for 'repeat' infections in the control group. In our study, however, it would neither be feasible to conduct STD testing, nor acceptable to do so in the context of a community-based study involving barbershops. As described in our second hypothesis, our intervention is designed to directly influence a set of theoretically derived variables, which in turn are expected to influence sexual risk. These mediating variables include intrapersonal variables such as condom use and HIV testing attitudes, self-efficacy, and subjective norms, as well as perceived skills in communication and negotiation skills around safer sex. These measures are typically ordinal in nature but analyzed as having interval level properties measures

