## **STATISTICAL ANALYSIS PLAN**

Project Title: Barbershop Talk: HIV Prevention for African American Heterosexual Men

NCT Number: NCT01980771

Date of document: 8/16/18

To describe study sample characteristics across groups at baseline and follow-up and in relation to condomless sex, the  $\chi^2$  test for categorical variables and the independent samples t-test for group differences in continuous variables were utilized. From the original list of measured variables, only those covariates that were associated at  $p < 0.05$  with baseline report of condomless sex or on which there were imbalances between the BTWB intervention and control groups at baseline, were included. Generalized mixed-effects models were used to estimate between-group differences at the participant level, taking into account the hierarchical data structure, with men clustered by barbershop. Differences between the BTWB intervention and control groups in changes in the outcomes were analyzed on an intention-to-treat basis. A binary logistic regression model was used to examine changes in condomless sex, with the six-month value modelled as the outcome and experimental group as the predictor, while controlling for barbershop site of recruitment (random effect), the baseline value of condom use (fixed effect), and covariates (fixed effects). Interaction terms between the covariates and experimental group assignment were tested for statistical significance in a stepwise approach. Data were analyzed using SAS PROC GLIMMIX, version 9.4, 2013.

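### Scored over six months as worded, the main outcome repeats the entry criteria at baseline and dilutes the 3-month comparison; the primary 6-month comparison is not contaminated

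*Protocol*

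**What the plan says.** Under Participants, the protocol admits men who report "two or more partners in the past six months, unprotected sex with a woman in the past six months". Under Program Evaluation, the main outcome for Hypothesis 1 is the proportion of "respondents who report two or more partners in the last six months and report unprotected sex during this time". Later in that section, after the list of other risk measures, it says: "Behaviors will be assessed over the previous three months". The sample-size calculation (Study design and sample size) also uses three months, namely "two or more sexual partners in the past three months plus at least one episode of unprotected vaginal or anal sex", and gives 42% as the pilot rate on that definition.

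The baseline interview follows screening and consent and precedes the program. Later assessments are at "3- and 6-month follow-up from the date of completion of the" program. Hypothesis 1 predicts "lower levels of sexual risk behavior at a 3 and 6 month follow-up". Data analysis puts the primary outcome at 6 months.

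The SAP models condomless sex at six months. Its model terms include "the baseline value of condom use (fixed effect"). It keeps covariates that are related to condomless sex at baseline (p < 0.05) or unbalanced between the arms. It states no look-back window.

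**The concern.** The documents give two windows for the same kind of outcome, and the sentence that defines the main outcome uses six months. A team that settles the conflict by following that sentence meets two practical problems.

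The first is at baseline. The outcome would ask again what the screener has just required, so it could hardly differ between men. A baseline measure that does not vary cannot improve precision and cannot be used to screen covariates.

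The second is at the 3-month visit. The look-back would reach behind the program into a period that the intervention could not have changed. Behavior common to both arms would be mixed into the outcome, and the 3-month part of Hypothesis 1 would be pulled toward no difference.

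**Working it through.** **1. The plan's own figures.** The inputs, all from the sample-size section, are a 42% control rate, a 12-point reduction, ICC 0.03, 23 men per shop and 15 shops per arm.

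- Intervention rate: 42 - 12 = 30%. Relative reduction: 12/42 = 28.6%, which the plan rounds to 29%.
- Design effect: 1 + (23 - 1) x 0.03 = 1.66. Men per arm: 15 x 23 = 345. Effective number per arm: 345/1.66 = 207.8.
- Two-sided 5% test of 42% v 30% on 207.8 per arm (normal approximation): power about 72%, against the stated 80%.

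That shortfall is a separate matter. The 72% serves here only as the yardstick for step 4.

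**2. Baseline.** Set the definitions side by side:

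- Entry: two or more partners, six months. Outcome: two or more partners, six months.
- Entry: unprotected sex with a woman, six months. Outcome: unprotected sex, six months.

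Entry implies outcome. The baseline interview comes directly after screening and consent, so the two windows nearly coincide. Baseline prevalence is 100% by definition, apart from men whose screener and baseline answers disagree. The SAP's variable is condomless sex, not the composite. Unprotected sex in six months is itself an entry criterion, so a yes/no version on that window would not vary either.

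**3. Follow-up windows.** Time is in months from program completion. The pre-program share of a six-month window is (6 - visit month)/6.

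| Visit | Six-month window | Pre-program share | Three-month window | Pre-program share |
|---|---|---|---|---|
| Month 3 | -3 to 3 | 3/6 = 50% | 0 to 3 | 0% |
| Month 6 | 0 to 6 | 0/6 = 0% | 3 to 6 | 0% |

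**4. Illustration of the dilution at month 3.** Let p0 be the share of men who meet the composite in the three months before program completion, taken as equal in both arms. Assume that the three months afterwards have rates of 42% v 30%, independent of the earlier block. A man is positive if either block is positive, so the rate in each arm is p0 + (1 - p0) x (post-program rate), and the difference is 12 x (1 - p0) points.

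- p0 = 42%: control 0.42 + 0.58 x 0.42 = 66.4%; intervention 0.42 + 0.58 x 0.30 = 59.4%; difference 7.0 points; power about 31%.
- p0 = 50%: difference 6.0 points; power about 26%.
- p0 = 70%: difference 3.6 points; power about 15%.

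Power uses the same 207.8 per arm.

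**5. Without independence.** Let d1 be the post-program difference among men who were positive in the pre-program block, and d0 the difference among the rest. Then 12 = p0 x d1 + (1 - p0) x d0. The month-3 difference is (1 - p0) x d0 = 12 - p0 x d1. What is lost is the effect in men with recent risk behavior. If d1 = 12 and p0 = 42%, the result is 12 - 5.04 = 6.96, as above. If d1 = 0 nothing is lost, and if the whole effect lies in those men nothing remains.

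This treats the six-month composite as the union of two three-month composites. A man with one partner in each block could also be positive, and that can move the difference either way.

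**The case against.** The strongest reply is that six months may be a drafting slip. The main-outcome text attaches a formative-work rate of just over 40%, which fits the 42% of the three-month definition, and three months appears twice elsewhere. With three months, neither problem arises. This stands as a reason to expect that three months was meant. It does not settle the matter, because the six-month wording is attached to the main outcome itself and the three-month sentence follows the list of other measures.

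It can also be said that the SAP's baseline variable need not be a yes/no item. Condom-use consistency is among the listed measures and could vary. Covariates can also enter through imbalance between the arms, and the SAP's account of associations with baseline condomless sex implies that it did vary. All of this stands, so the baseline point is conditional on a yes/no item over six months.

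Some stronger readings are tempting, but the documents do not support them:

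- A reader might infer that the primary result is biased. At month 6 a six-month window contains no pre-program time, and a constant baseline does not bias a randomized comparison.
- A reader might infer that every man positive at entry is bound to be positive at month 3. Only behavior in roughly the last three months before the program carries over; the entry window is longer.
- A reader might infer that a six-month window upsets the order of mediators and outcome. Nowhere do the documents commit to predicting the 6-month outcome from 3-month mediators. Hypothesis 2 tests the mediators as outcomes at both visits.

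**Conclusion.** The point holds if the six-month wording is applied. The baseline composite is then fixed at 100% by eligibility, apart from inconsistent answers. The cost is lost precision and a covariate screen with little or nothing to work on. At the 3-month visit half of the window predates the program, and the contrast is diluted whenever the program works in men with recent risk behavior.

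The overlap and the baseline identity follow from the documents. The size of the dilution does not. Seven points instead of 12 is an illustration that rests on 42% v 30% after the program, p0 = 42% in both arms and independence between blocks. Independence is unlikely for the same men, and the documents give no value for p0 under these entry criteria; 50% and 70% only show a range.

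The 6-month primary comparison is not contaminated. This is a cheap and worthwhile correction to the outcome definition, not a flaw that undermines the main result.

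**What to change.** Keep the six-month items for eligibility only. In Program Evaluation, define the main outcome as two or more partners plus at least one episode of unprotected vaginal or anal sex, both over the previous three months, at baseline, 3 months and 6 months. State the same window in the SAP for condomless sex and for its baseline value. This matches the sample-size definition and its 42% planning rate, leaves room for baseline variation, and keeps both follow-up windows after the program. If a six-month look-back is kept, report it at the 6-month visit only, as supportive.

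The cost is one sentence in the protocol and one in the SAP, with no new visit, and no new item if the interview already asks about three months. The drawbacks are a somewhat lower event rate than over six months, and that behavior in the first three months after the program is captured only at the 3-month visit.
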